#### **Timed-Up-and-Go [sec]**

The time-up-and-go is used because it is considered a valid and reliable measuring instrument for the evaluation of physical activity after hip and knee prostheses (Dobson et al. 2012). The subject is asked to rise from a chair while sitting and walk three meters, turn around and sit down again. The time spent on this task is measured in seconds. The measurement moments take place preoperatively, on the 4th postoperative day and 6 weeks postoperatively.

#### **Length of stay [days]**

The number of hospitalisation days (from admission to and with discharge) is counted and documented.

### **9.2.2 Assessment of secondary outcomes**

None available.

### **9.2.3 Assessment of other outcomes of interest**

None available.

### **9.2.4 Assessment of safety outcomes**

No corresponding parameters are collected.

#### **9.2.4.1 Adverse events**

-

#### **9.2.4.2 Laboratory parameters**

-

#### **9.2.4.3 Vital signs**

-

### **9.2.5 Assessments in subjects who prematurely stop the clinical investigation**

For the participants, there is no disadvantage in the event of an (arbitrary) discontinuation of study participation and no further interventions are necessary for follow-up treatment.

However, if study participation was discontinued due to an injury sustained during study participation, this will be recorded and reported to the sponsor, the head of the research laboratory, the study leader and the supervisor of the study. The report is then sent to the business liability insurance of Thim van der Laan AG in order to ensure the appropriate follow-up treatment.

The following are recorded:

- Date and time of the incident
- Course of the incident

- Persons involved & witnesses
- Study ID (issued by the CEC)
- Personal details of the person concerned (if not previously recorded)

### **9.2.6 Follow-up of the subjects after the regular termination of the clinical investigation**

Since the Game Ready GR PRO 2.1 thermotherapy device used is only used in the context of the intended use, no additional care of the subject is required after the end of his or her participation in the clinical trial, nor are arrangements made for subsequent care.

### **9.3 Procedures at each visit**

All rounds take place on the premises of the Regional Hospital Surselva AG.

#### **9.3.1 Single measurement**

The project consists of multiple visits with a total duration of 850 minutes, which takes place as follows:

#### **9.3.2 Multiple visits**

Responsibility for conducting the study and protecting participants Responsibility: [name]

### **1. Subject Information & Informed Consent**

The "Visit 1: Screening" includes the following steps: The test subjects are subjected to a screening before being accepted participation in the study is comprehensively informed about the process and possible risks. You will also receive the information in written form and have the opportunity to ask questions. The declaration of consent explains to you what your rights and obligations are when participating and that you may withdraw from participation at any time without giving reasons, without any disadvantage to you. More detailed information can be found in chap. 2.7. Responsibility: [name], [name]

### **2. Running the Test Log**

**Visit 1:** Screening describes the collection of baseline values (preoperatively) as well as any further information, written consent, examination of all inclusion/exclusion criteria, and the health questionnaire.

**Start of the cooling intervention:** In addition to the usual physiotherapeutic treatment: Daily Cooling and compression. A detailed description of the intervention can be found in chap. 8.1.1.

**Visit 2 and 3:** The measurements are carried out in the same way as the test protocol and the data is collected.

Responsibility: Research staff of the University of Applied Sciences and Arts Southern Switzerland

### **3. Indemnification and Conclusion**

After completion of the measurements (6 weeks postoperatively), the subject will receive the compensation due according to the information in the advertisement: a flat rate of CHF 50 after completion of the measurements.

Responsibility: Research staff of the University of Applied Sciences and Arts Southern Switzerland

## **10. SAFETY**

### **10.1 Definition and Assessment of (Serious) Adverse Events and other safety related events**

**Adverse Event (AE)** (Art. 2 para. 57 MDR)

Any untoward medical occurrence, unintended disease or injury or any untoward clinical signs (including an abnormal laboratory finding) in subjects, users or other persons whether or not related to the MD.

**Serious Adverse Event (SAE) (Art. 2 para. 58 MDR)** Any

adverse event that led to any of the following:

- (a) Death
- (b) serious deterioration in the health of the subject that resulted in any of the following:
  - (i) life-threatening illness or injury,
  - (ii) permanent impairment of a body structure or a body function,
  - (iii) hospitalisation or prolongation of patient hospitalisation,
  - (iv) medical or surgical intervention to prevent life-threatening illness or injury or permanent impairment to a body structure or a body function,
  - (v) chronic disease,
- (c) foetal distress, foetal death or a congenital physical or mental impairment or birth defect.

Note: planned hospitalization for pre-existing condition, or a procedure required by the CIP, without a serious deterioration of the health status of the subject, is not considered an SAE

**Device deficiency (Art. 2 para. 59 MDR)**

Inadequacy of a medical device related to its identity, quality, durability, reliability, safety or performance, of an investigational device, including malfunction, user errors and inadequate information supplied by the manufacturer.

**Malfunction (ISO14155)**

Failure of an investigational device to perform in accordance with its intended purpose when used in accordance with the instructions for use or the CIP.

**Device deficiency with Serious Adverse Device Effect (SADE) potential (Art. 80 para. 1 letter c MDR; ISO14155)**

Any device deficiency that might have led to a serious adverse event if appropriate action had not been taken, intervention had not occurred, or circumstances had been less fortunate.

**Adverse Device Effect (ADE) (ISO14155)**

Adverse event possibly, probably or causally related to the use of an investigational device or procedures.

**Serious Adverse Device Effect (SADE) (ISO14155)**

Adverse device effect (ADE) that has resulted in any of the consequences characteristic of a serious adverse event.

**Unanticipated Serious Adverse Device Effect (USADE) (ISO14155)**

Serious adverse device effect (SADE) which by its nature, incidence, severity or outcome has not been identified in the current version of the risk analysis report.

**Causal Relationship of SAE (MDCG 2020-10/1)**

A causal relationship towards the medical device or the procedure of the investigation should be rated by the PI and the Sponsor as follows:

- **Not related:** The relationship to the device or procedures can be excluded.
- **Possible:** The relationship with the use of the investigational device is weak but cannot be ruled out completely. Alternative causes are also possible.
- **Probable:** The relationship with the use of the investigational device seems relevant and/or the event cannot reasonably be explained by another cause.

- **Causal relationship:** The serious event is associated with the investigational device or with procedures beyond reasonable doubt.

## 10.2 Adverse events categorization

The adverse events are categorized by the PI and the Sponsor using the following algorithm: Does the AE meet the seriousness criteria?

- No, it is not serious
  - Is the relationship to the device or the procedure possible, probable or causal?
  - No: non-related AE
  - Yes: ADE
- Yes, it is serious: SAE
  - Is the relationship to the device or the procedure possible, probable or causal?
  - No: non-related SAE
  - Yes: SADE
- Is it anticipated (within expected type, severity and frequency of the complications)?
  - No: unanticipated SADE (USADE)
  - Yes: anticipated SADE (ASADE)

## 10.3 Documentation and reporting in Medical Device Category A clinical investigations

Device deficiencies (DD) and all **adverse events (AE)** including all **serious adverse events (SAE)** are collected, fully investigated and documented in the source document and appropriate case report form (CRF) during the entire investigation period, i.e. from patient's informed consent until the last CIPspecific procedure, including a safety follow-up period.

- Documentation of AEs (including SAEs) by the PI includes diagnosis or symptoms, start and stop dates of event, event treatment, event resolution, assessment of seriousness and causal relationship to MD and/or investigation procedure (Art. 32 ClinO-MD, ISO14155).
- Documentation of DDs by the PI includes description of event, start date, investigational device information, action taken with regard to the investigational device, and whether the DD led to an AE. The Sponsor shall review all DDs and determine and document in writing whether they could have led to a SAE (DD with SADE potential) (Art 32. ClinO-MD, ISO14155).

The project works with a CE-certified product. It is a study with 30 or fewer subjects. The study focuses on basic findings. The study aims to gain fundamental knowledge in the field of cryotherapy in combination with compression. The monitoring for quality assurance is carried out by [name], PhD.

### 10.3.1 Foreseeable adverse events and anticipated adverse device effects

The following foreseeable serious adverse events and product defects may occur:

- tissue damage due to improper or too long use than described by the manufacturer,
- burning, itching, increasing swelling, pain, blisters, increasing redness, discoloration and other visible changes during treatment,
- Change in wound conditions (if the wrap is not applied over the bandage or clothing),
- Risk of electric shock (if other power supplies are used, housing parts are removed, or damaged cables and connecting hoses are used) and
- Device damage (if there is no or too hot water in the ice box, the device is lifted up by the lid, or wraps from other manufacturers have been used).

Participants who complain of ongoing adverse events after graduation/discontinuation of their studies will be contacted by telephone two weeks after graduation and asked about their state of health. If the

undesirable events still exist, the participants will be called up for an additional visit to the Surselva Regional Hospital AG. During this visit, the ongoing events are assessed and documented.

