## 7.4 Criteria for withdrawal / discontinuation of subjects

If a participant withdraws from the study, the allocation lot is returned to the pot in a new envelope and a new participant is sought.

The already completed consent form is kept in the locked filing cabinet. In the event of a revocation of consent, the data and samples already collected must be included in the evaluation for scientific and security reasons. Only after the analysis are they anonymised (Art. 9 ClinO).

The conditions for the termination of the experiment were described in chap. 5.4.

There is no disadvantage for the participants in the event of a termination of the Study participation.

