## **8.2 Discontinuation or modifications of the intervention**

No further side effects are expected from participation in the study, as it is not an invasive method or drug intervention. As in chap. 8.5, the predefined inclusion and exclusion criteria as well as the health questionnaire are used to ensure safe participation. However, if reasons arise, the study participant reserves the right to withdraw from the study early. The test person reserves the right to exclude a participant from the study for the following reasons: safety aspects (feeling unwell, dissatisfaction of the participant), occurrence of one of the predefined exclusion criteria, at the request of the participant, revocation of consent (also possible without justification). Further information in this case can be found under chap. 9.2.5 and 7.4.

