## **8.4 Data Collection and Follow-up for withdrawn subjects**

The medical follow-up of subjects who drop out of the examination prematurely is described in chapters 9.2.5 and 9.2.6. There is no disadvantage for the participants if they discontinue their participation in the study and no further interventions are necessary for follow-up treatment.

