
Visit 1: Screening and baseline preoperatively: information, written consent, examination of /Exclusion criteria, health questionnaire
 
Physical Function [Score]
 
Joint circumference [mm]
 
Range of motion [degrees]
 
Skin temperature [°C]
 
Visual Analog Pain Scale [cm]
 
10-meter walk test [sec]
 
Timed-up-and-Go [sec]
	60 min

Daily cooling intervention
 
In addition to the usual physiotherapeutic treatment: Daily Cooling and compression. One detailed treatment description can be found in chap. 8.1.1.
	
2x daily one treatment of 60 min = 120 min per day
 
4x 120 min per day = 480 min per stay

Visit 2: Follow up 4th postoperative day
 
Physical Function [Score]
 
Joint circumference [mm]
 
Range of motion [degrees]
 
Skin temperature [°C]
 
Visual Analog Pain Scale [cm]
 
Patient satisfaction [cm]
 
10-meter walk test [sec]
 
Timed-up-and-Go [sec]
	30 min

Visit 3: Follow up 6 weeks postoperatively  Physical Function [Score] Joint circumference [mm] Range of motion [degrees] Skin temperature [°C] Visual Analog Pain Scale [cm] 10-meter walk test [sec] Timed-up-and-Go [sec] Length of stay [days] Morphine consumption [number]	40 min
Total time commitment:	610 min

Any adverse events must be recorded during each visit. These possible time expenditures are not included in the test protocol.

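### A participant who leaves the study early gets no unprompted safety contact, so an adverse event that first appears afterwards is recorded only if someone brings it to the study's notice

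*Combined protocol and SAP*

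**What the plan says.** Section 10.3 sets the collection window for all adverse events. It opens at informed consent and runs "until the last CIPspecific procedure, including a safety follow-up period". The length of that follow-up period, the method of contact and the participants it covers are not stated.

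Routine capture is tied to visits. Section 9.1 says: "Any adverse events must be recorded during each visit". After surgery the scheduled visits are the 4th postoperative day and 6 weeks.

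The one follow-up contact spelled out is in 10.3.1: "Participants who complain of ongoing adverse events after graduation/discontinuation of their studies will be contacted by telephone two weeks after graduation". If the events persist, the participant is called in for an extra hospital visit, where they are assessed and documented.

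For early leavers, 8.2 allows the study "to exclude a participant from the study for the following reasons: safety aspects (feeling unwell, dissatisfaction of the participant"), among other grounds. Section 8.4 then says: "The medical follow-up of subjects who drop out of the examination prematurely is described in chapters 9.2.5 and 9.2.6". Of those two sections:

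- 9.2.5 states that "if study participation was discontinued due to an injury sustained during study participation, this will be recorded and reported to the sponsor", and otherwise foresees no follow-up treatment.
- 9.2.6 concerns regular completion and says that "no additional care of the subject is required after the end of his or her participation in the clinical trial".

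**The concern.** The plan promises to collect all adverse events but relies on visits to find them. A participant who leaves also leaves the visit schedule. The cross-reference in 8.4 suggests that follow-up of leavers is dealt with elsewhere, yet the sections it names do not schedule any.

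What is at stake is the completeness of the safety record for a group that may not be neutral with respect to safety, since feeling unwell is one of the listed reasons for exclusion. A late event in such a person, such as tissue damage or a change in the wound (both named as foreseeable in 10.3.1), could go unrecorded. The case report form record under 10.3, and the serious device effects listed in the annual safety report under 10.3.2, can hold only what the study learns of.

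**Working it through.** The plan gives no figure to reproduce. The check follows one participant who fully withdraws or is excluded before the 6-week visit and asks of each section whether it provides a contact that does not depend on a complaint.

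- **9.1 (visits).** Adverse events are recorded at visits. Full withdrawal removes those that remain. None is left.
- **7.4 (withdrawal).** It deals with the lot ("the allocation lot is returned to the pot in a new envelope and a new participant is sought"), the consent form and the data already collected. No contact.
- **8.2 and 8.4.** They refer to 7.4, 9.2.5 and 9.2.6. No contact of their own.
- **9.2.5.** It covers an injury that happened during participation and caused the discontinuation, so an event before leaving. No later contact.
- **9.2.6.** It covers those who finish as planned, and arranges no later care. No contact.
- **10.3.1.** A call, then a visit if needed, but only for those who complain of ongoing events. The sentence mentions discontinuation, yet its two-week clock is stated only from what the translation calls graduation, so a leaver has no clear call date.
- **6.3 and 10.3.2.** Both act on events that are already known. The 24-hour reporting clock starts when the investigator learns of the event.
- **10.3.** It names a safety follow-up period but gives it no content for a leaver who has not complained.

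Scheduled unprompted safety contacts after full withdrawal are therefore 0, whether the person leaves before or after the day-4 visit. With one unconditional call the number is 0 + 1 = 1.

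The time involved can be illustrated. Suppose someone leaves straight after the day-4 visit and would have been seen at 6 weeks (6 × 7 = day 42).

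- Time with no scheduled contact, up to when that visit would have taken place: 42 − 4 = 38 days.
- A call two weeks after discontinuation falls on day 4 + 14 = 18 and asks about the first 14 of those 38 days.
- The remaining 42 − 18 = 24 days still depend on patient report.

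Three kinds of event are outside the gap:

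- An event that causes the withdrawal is documented under 10.3.
- An event the participant already complains of on leaving triggers the 10.3.1 call, which asks about the state of health and can pick up a worsening.
- An event in someone who only stops the cooling (5.4) but stays in the study is recorded at the remaining visits.

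What remains is an event that first appears after full withdrawal, or that was never mentioned before it.

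**The case against.** The strongest case for leaving the plan as it is has four parts.

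**Setting.** Treatment is given in hospital in the first postoperative days, and hospital physiotherapists carry out and document the standard therapy (8.1.2). Someone who leaves before day 4 is probably still an inpatient there, so staff may notice a problem. This reduces the gap in the first days. It does not close it: the plan writes no route from ward records of a withdrawn patient to the case report form, and inpatient care would not normally reach to 6 weeks.

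**Proportionality.** The device is CE-marked, the study is category A1, and participants may leave at any time without giving reasons. Many of the foreseeable effects in 10.3.1 are tied to use of the device. Contact triggered by a complaint is a defensible choice. This stands as a reason to rate the point minor.

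**Unseen material.** The subject information and the data collection form are appendices that are not shown. Either may add something. An instruction to report later events would still rely on the patient.

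**The follow-up period in 10.3.** The plan does not say that the 10.3.1 call is all of it. That is right. The point is that nothing else is described.

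A reader might also infer more than the documents support:

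- That no safety follow-up is foreseen. Section 10.3 names one.
- That any worsening after withdrawal is missed. The existing call can pick up the worsening of an event already complained of.
- That device deficiencies would go unlisted. A leaver no longer uses the device, so a new deficiency can hardly arise in that person's treatment.
- That trial results would be biased by this gap. No safety parameters are collected as outcomes (9.2.4), and 11.5 already leaves non-completers out of the final analysis.

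**Conclusion.** The point holds, as a minor and cheaply remedied gap. For a participant who fully withdraws or is excluded before the 6-week visit, the plan schedules no unprompted safety contact. An adverse event with first onset after that, or never mentioned before it, is captured only if the patient or hospital staff bring it forward.

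The number of people affected cannot be estimated, because no drop-out rate is given. A share of the 28 planned participants would not measure the loss either, since it says nothing about how many events go unseen.

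The conclusion rests on two assumptions: that full withdrawal or exclusion ends the study visits, which the documents imply but do not state, and that the appendices not shown contain no scheduled contact for leavers.

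**What to change.** In 10.3.1, provide that every participant in either group who withdraws or is excluded before the 6-week visit is telephoned two weeks after the day of discontinuation, whether or not a complaint was made, unless he or she refuses contact, and is asked about any adverse event since leaving. Keep the additional hospital visit for events that are still ongoing, and keep the complaint-triggered call for those who complete the study. Name the new call in 10.3 as the safety follow-up for early leavers, and refer to it in 8.4 and 9.2.5.

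The cost is wording in four sections and one short call per early leaver, using a procedure the plan already has. Some leavers will decline, and events after the call still depend on the patient reporting them, so the change narrows the gap without closing it.

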### **10.3.2 Reporting of Safety related events**

#### **Reporting to the Sponsor:**

All SAEs, device deficiencies and health hazards that require measures are reported to the Sponsor by the PI (or authorized designee) within 24 hours after becoming aware of the event. Device deficiencies are assessed regarding their potential to lead to an SAE. DD are assessed regarding their potential to lead to an SAE.

#### **Reporting to the Competent Ethics Committee:**

The Sponsor reports to the CEC promptly any serious adverse event which has a causal relation with the MD, comparator or procedure/test method or where a causal relation appears to be possible (Art. 33 ClinO-MD).

In order to ensure prompt notification, the Sponsor may initially submit an incomplete notification.

If safety and health hazards that require measures must be taken immediately during the conduct of the investigation, the Sponsor notifies the CEC within 2 days of these measures and the circumstances which made them necessary (Art. 34 ClinO-MD).

Periodic safety reporting (Art. 35 ClinO-MD):

An Annual Safety Report (ASR) is submitted by the Sponsor to the CEC, yearly. The ASR contains a list of all SADEs and DDs and a report on their degree of seriousness, causal relationship with the MD and procedure and on subjects' safety.

Other reporting is done according to provisions of MD vigilance as per Art. 87-90 MDR (Art. 33 para. 4.b ClinO-MD) and Art. 67 MedDO.

